### 7.1.4 Locoregional therapy

Any subject receiving locoregional therapy, including surgery, while on study that directly affects one or more of the target lesions selected at baseline will be identified. A subject with a subsequent response or SD will be considered to be non-evaluable at all disease assessments that occur on or after the date of locoregional therapy. Otherwise, the subject will be assessed ignoring the locoregional therapy.

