#### **4.7.2 Prohibited Concomitant Medications**

Subjects must be instructed not to take any medications, including over-the-counter products, without first consulting with the investigator. The following concomitant medications are prohibited:

- Any investigational anticancer therapy
- Any concurrent chemotherapy, radiotherapy (except palliative radiotherapy), immunotherapy, biologic or hormonal therapy for cancer treatment. Concurrent use of hormones for noncancer-related conditions (eg, insulin for diabetes and hormone replacement therapy) is acceptable.
- Immunosuppressive medications including, but not limited to systemic corticosteroids at doses exceeding 10 mg/day of prednisone or equivalent, methotrexate, azathioprine, and tumor necrosis factor-alpha blockers. The following are exceptions:
  - Use of immunosuppressive medications for the management of investigational product-related AEs or in subjects with contrast allergies is acceptable.
  - Use of inhaled, intranasal, or topical corticosteroids is permitted.
  - Temporary courses of corticosteroids for treatment of underlying or concurrent illness or in the setting of palliative radiotherapy may be permitted upon discussion with the medical monitor.
- Live attenuated vaccines during the study through 180 days after the last dose of study drug
- Herbal and natural remedies should be avoided

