### **3.4.2.4 Progression-free Survival**

Progression-free survival (PFS) is defined as the time from randomization until the first documentation of a disease progression or death due to any cause, whichever occurs first, regardless of whether the subject receives subsequent anticancer treatment prior to progression. Subjects who have no documented progression and are still alive at the time of analysis will be censored at the time of the latest date of assessment from their last evaluable RECIST v1.1 assessment. PFS is defined in months as follows:

$$\text{PFS (months)} = (\text{Date of PD/death or censoring} - \text{Date of randomization} + 1) / (365.25/12),$$

The censoring guidance and the date of PD/death or censoring are given in the table below. The number and percentage of subjects experiencing a PFS event and Kaplan-Meier plots of PFS will be presented by treatment group. The median PFS and its 95% CI will be estimated using the Kaplan-Meier method. The proportion of subjects progression-free and alive at 12

months (PFS-12) and associated 95% CI will be estimated using the Kaplan-Meier method. Additional PFS landmarks to be included in the final analysis are PFS-18, PFS-24, and PFS-36.

The difference in PFS between each experimental arm and control arm will be tested for significance by using a stratified log-rank test on histology (adenocarcinoma vs non-adenocarcinoma). The log-rank test will be carried out with the Breslow method for handling ties. The hazard ratio (HR) (experimental vs. control) with two-sided 95% CI will be estimated by stratified Cox regression model on histology with ties handled by the Efron method ([Efron et al, 1977](#)).

The comparison of PFS-X (X=12, 18, 24, 36 months) between each experimental arm and control arm will be performed by normal approximation under complementary loglog (cloglog) transformation ([Klein et al, 2007](#)). The test statistic shown below asymptotically follows a chi-square distribution with one degree of freedom under the null hypothesis  $H_0: S_1(t) = S_2(t)$ .

$$X^2 = \frac{\left( \log(-\log(\hat{S}_1(t))) - \log(-\log(\hat{S}_2(t))) \right)^2}{\hat{\sigma}_1(t)^2 / \left( \log(\hat{S}_1(t)) \right)^2 + \hat{\sigma}_2(t)^2 / \left( \log(\hat{S}_2(t)) \right)^2}$$

where

- $\hat{S}_k(t)$ , with  $k = 1, 2$  is the Kaplan-Meier estimate of the survival function for the  $k$ th treatment group

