**Table 3.4.1      Summary of Censoring Guidelines for PFS**

Situation	Date of PD/Death or Censoring	PFS Outcome
Documented Progressive Disease (PD) or death	Date of earliest sign of PD or death, whichever comes first	Event (unless the censoring rule specified below)
Death or PD immediately after $\geq 2$ consecutive missed or non-evaluable disease assessments as per the protocol specified assessment schedule	Date of last progression-free disease assessment prior to missed or non-evaluable assessments, or randomization, whichever occurred last	Censored
No PD or death at time of analysis or lost to follow-up	Date of last evaluable progression-free disease assessment	Censored
No tumor assessment at baseline and no evidence of PD at first post-baseline disease assessment OR No tumor assessment post-first dose, and no death prior to second scheduled post-baseline disease assessment	Date of randomization	Censored

PD = progressive disease; PFS = progression-free survival.

Subjects having missing lesion data at baseline or no disease assessments post-first dose of IP will have PFS censored at the date of randomization unless the subject dies prior to the second scheduled post-baseline disease assessment in which case the death date will qualify as a PFS event.

If a subject has two or more consecutive completely missed or non-evaluable assessments followed immediately by death or an assessment showing radiologic disease progression, then the subject will be censored for PFS. PFS will be censored at the date of randomization or the last progression-free disease assessment prior to the missed or non-evaluable assessments, whichever occurred last.

If a subject has two or more consecutively missed or non-evaluable assessments followed by an assessment showing no radiologic disease progression, then the assumption will be that the subject did not progress during the missed or non-evaluable assessments.

The length of gap (in number of days) to determine two or more consecutive assessments is defined as the following:

- 126 days during the first 12 months (A 8-week disease assessment interval plus a 7-day window for each assessment).

- 182 days from month 12 to month 24 (A 12-week disease assessment interval plus a 7-day window for each assessment).
- 422 days after month 24 (A 6-month disease assessment interval plus a 4-week window for each assessment).

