#### 7.1.1 Target Lesion Response

Target lesion response will be programmatically derived on the data collection instrument once RECIST v1.1 criteria are applied to the site personnel recorded target lesion measurements.

Possible values include:

- CR – Complete Response
- PR – Partial Response
- SD – Stable Disease
- PD – Progressive Disease
- NE – Non-evaluable
- NA – Not Applicable (*set value for all post-baseline disease assessments only if no target lesions are identified at baseline*)

The derivation for target lesion response is as follows (*please note the order of the algorithm below is important*):

1. If “Any Target Lesions Present” equals “No” on the *Target Lesions – Baseline* CRF, then all post-baseline “Target Lesion Response” equals “NA”.
2. Else, if “Percent Change from Nadir Sum of Diameters” is greater than or equal to 20% and the absolute increase from the nadir (defined as the “Total” for each post-baseline disease assessment minus the “Nadir Sum of Diameters”) is greater than or equal to 5 mm, then “Target Lesion Response” equals “PD”.
3. Else, if “Not Done” is selected, or “Measurement” is left blank, or “Lesion no longer Measurable” is selected and equal to “NE”, or “Lesion Intervention” is selected for any Target Lesion identified at Baseline, then “Target Lesion Response” equals “NE”.
4. Else, if “Total Non-Lymph Node” equals “0” and all Lymph Node Target Lesion “Measurements” are less than “10” individually, then “Target Lesion Response” equals “CR”.

Note: This step requires examining “Measurements” separately for Target Lesions with “Lymph Node” equal to “Yes” and “No”.

5. Else, if “Percent Change from Baseline Sum of Diameters” is less than or equal to -30%, then “Target Lesion Response” equals “PR”.
6. Else, “Target Lesion Response” equals “SD”.

If a subject has a missing tumor measurement at a disease assessment for 1 or more target lesions, the sum of diameters (longest for non-nodal lesions, short axis for nodal lesions) will be reported for the remaining target lesions. These data will be used to indicate radiologic disease progression if the sum of diameters for the observed lesions increases at least 20% from the nadir sum of diameters of all target lesions and demonstrates at least a 5 mm absolute increase from the nadir sum of diameters of all target lesions, in spite of the missing data (or if other criteria for PD are met).

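### Scans made non-evaluable by target-lesion locoregional therapy feed the SAP's two-assessment censoring rule, so some observed progressions and deaths are censored for PFS and DoR in subjects scanned on schedule

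*SAP*

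**What the plan says.** Protocol 4.7.2 prohibits concurrent cancer treatment but makes an exception within its radiotherapy entry: "radiotherapy (except palliative radiotherapy". A subject can therefore receive local radiation on study.

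SAP 7.1.4 deals with on-study locoregional therapy, surgery included, that "directly affects one or more of the target lesions selected at baseline will be identified". For later stable disease (SD) or response the rule is "A subject with a subsequent response or SD will be considered to be non-evaluable at all disease assessments" from the therapy date on. The section ends: "Otherwise, the subject will be assessed ignoring the locoregional therapy".

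SAP 7.1.1 step 3 does the same at lesion level. Target response becomes NE when the lesion-intervention box "is selected for any Target Lesion identified at Baseline". SAP 3.4.2 makes Appendix 7.1 the derivation guidance for the efficacy analyses other than OS.

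The text under SAP Table 3.4.1 sets the censoring rule: "If a subject has two or more consecutive completely missed or non-evaluable assessments followed immediately by death or an assessment showing radiologic disease progression", the subject is censored at the later of randomization and the last progression-free assessment before that run. SAP 3.4.2.2 gives DoR the same event or censoring date as PFS.

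SAP 3.4.2.4 nevertheless defines PFS as counting progression or death "regardless of whether the subject receives subsequent anticancer treatment prior to progression". Protocol 4.8.3 has an equivalent clause and describes censoring only for subjects alive and progression-free at data cutoff.

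**The concern.** The two-assessment rule exists for gaps in observation, where the date of progression is uncertain because nobody looked. Here the subject was imaged at every visit, and the gap is created by recoding.

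Whether the eventual progression or death counts then depends on how long the subject stayed free of progression after the therapy. Early failures are kept, and later ones are censored at a date before the therapy. That makes the censoring outcome-dependent.

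The SAP has a clause that treats a subject as progression-free through a gap if a later assessment shows no progression. It cannot help on a plain reading, because SAP 7.1.4 makes every later SD or response scan NE as well.

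At stake are the secondary comparisons of PFS, the PFS landmarks and DoR. The trial is open-label, so local therapy could be used differently between arms.

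**Working it through.** **Reproducing the SAP's gap lengths.** Gap = 2 × (interval + window), with the intervals and windows given under Table 3.4.1:

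- Months 0–12: 2 × (56 + 7) = 126 days
- Months 12–24: 2 × (84 + 7) = 182 days
- After month 24: 2 × (183 + 28) = 422 days

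All three match the SAP.

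**Applying 7.1.4 and then Table 3.4.1.** Day 0 is the last evaluable scan, therapy to a target lesion follows it, and later SD scans become NE. With k NE scans, progression at the next scheduled scan falls on day (k + 1) × interval.

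| NE scans before PD | 8-weekly (limit 126) | 12-weekly (limit 182) | 6-monthly (limit 422) | PFS outcome |
|---|---|---|---|---|
| 0 | day 56 | day 84 | day 183 | event |
| 1 | day 112 | day 168 | day 366 | event |
| 2 | day 168 | day 252 | day 549 | censored at day 0 |
| 3 | day 224 | day 336 | day 732 | censored at day 0 |

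Counting assessments and counting days agree in every row. They can disagree for deaths between scans: NE scans on days 56 and 112 with death on day 120 is censored by count, but lies within 126 days.

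**Worked case.** Scans are 8-weekly, SD at weeks 8 and 16, therapy at week 22.

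- PD at week 24 or 32 is an event.
- PD at week 40 follows SD scans at weeks 24 and 32. It comes (40 − 16) × 7 = 168 days after the week-16 scan and is censored at week 16.
- PD at week 48 is 224 days after that scan and is also censored at week 16.

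A treated subject who never progresses is likewise cut back to week 16, because Table 3.4.1 uses the last evaluable progression-free assessment.

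**Illustration of size.** The documents give no prevalence of target-lesion therapy, so a range is assumed. Other inputs are exponential PFS with median 17.2 months (protocol 1.1), the protocol scan schedule and 60 subjects per arm. Further assumptions are 36 months of follow-up, 85% of events being progression and 15% death, and a therapy date uniform over year 1, unrelated to progression and applied only if it precedes progression.

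| Assumed prevalence | Events censored per 60 | Share of 45 events | PFS-12 |
|---|---|---|---|
| 0% | 0 | 0 | 0.637 |
| 2% | 0.6 | 0.6/45 = 1.3% | 0.634 |
| 5% | 1.4 | 1.4/45 = 3.1% | 0.634 |
| 10% | 2.8 | 2.8/45 = 6.2% | 0.629 |
| 20% | 5.3 | 5.3/45 = 11.8% | 0.619 |

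Among affected subjects, about 83% to 85% of PFS events are censored. The event rate per unit of follow-up rises by about 0.8% at 5% prevalence and 1.6% at 10%. The change is small because person-time is lost along with the events.

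**The case against.** The best defence has four parts.

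1. *The exception is disclosed.* Table 3.4.1 itself says that PD or death is an event unless a censoring rule applies. The clause on subsequent treatment can be read as saying only that therapy does not by itself censor. This softens the word contradiction, but the effect remains: therapy to a target lesion leads to censoring through the recoding, and nothing says that this was intended.
2. *The scans really are uninformative.* Once a target lesion has been treated locally, the sum of diameters no longer measures drug effect. This stands for response. It does not make a later new lesion, non-target progression or death unobserved.
3. *The trigger is narrow.* A reader might infer that any permitted palliative radiotherapy or surgery sets it off. It does not: the therapy must directly affect a baseline target lesion, and at least two NE scans must follow. Treatment of a newly appeared lesion comes after PD is already recorded. Surgery is foreseen by SAP 7.1.4, but protocol 4.7.2 neither lists it as prohibited nor expressly permits it.
4. *Other outputs limit the harm.* OS counts every death. SAP 3.4.3 says that investigator-reported outcomes are shown without censoring rules, but SAP 3.4.2.4 lists no such PFS analysis.

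A reader might also take the phrase about all assessments in 7.1.4 to make the later PD scan itself NE, so that the event vanishes. The rest of the SAP largely answers this. In 7.1.1 the PD test comes before the intervention step and the order is stated to matter. In 7.1.3, PD in any component or a new lesion gives overall PD. SAP 7.1.4 is itself conditional on later SD or response. A clarifying phrase is enough.

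**Conclusion.** The point holds as an inconsistency between SAP 7.1.4 and 7.1.1 step 3 on one side and the SAP's PFS definition on the other. It operates through Table 3.4.1 and extends to DoR. The affected subjects have complete imaging, and their events are censored early. The subjects are not dropped from the analysis.

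Two stronger inferences are not supported. One is that removing 2% to 10% of an arm's events would move the hazard ratio by a similar amount. That ignores the lost person-time: in the illustration about 6% of events go at 10% prevalence, while the hazard changes by only 1% to 2%. The other is that the rule inflates PFS. With timing unrelated to progression, PFS-12 moves slightly down, from 0.637 to 0.629 at 10% prevalence.

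These figures rest on the assumed prevalence, exponential PFS and neutral timing. If use differs by arm or therapy timing follows prognosis, the documents do not allow size or direction to be stated. ORR, the primary endpoint, is not affected by this PFS censoring, and PFS and DoR are secondary. The correction is worth making because the rule misclassifies observed events and is cheap to repair.

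**What to change.** In SAP 7.1.4 and 7.1.1 step 3, limit the locoregional-therapy and lesion-intervention recoding to best overall response, ORR, DCR, response dates and tumour-size derivations.

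In SAP 3.4.2.4, and for DoR through 3.4.2.2, state that:

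- a scan that is NE only because of locoregional therapy does not count toward the rule for two or more missed or non-evaluable assessments;
- a later RECIST progression or death is an event on its own date;
- the reference in 7.1.4 to all assessments excludes those that show PD.

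PFS under the current rule could be kept as an optional sensitivity analysis.

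The cost is about two sentences and one programming flag, with no new data. The small downside is that progression in a locally treated target lesion may be recorded somewhat later.

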### 7.1.5 Assignment of Dates of Disease Progression or Disease Response

For all analyses of endpoints resulting from an application of RECIST v1.1 to investigator assessed tumor measurements, there may be cases in which disease assessments span a series of dates. For establishing the start date of a subsequently confirmed response in which the disease assessment spans multiple days, the date of response assigned will be the latest date of evaluations corresponding to the disease assessment. The date of latest evaluation will also be assigned for a mid-study assessment showing SD as the date assigned for the purposes of censoring duration of response, TTP and PFS.

The date of PD will be the first date at which any objective diagnostic test provides data indicating PD. Specifically, for RECIST v1.1 the date of PD will be the earliest of the following 3 evaluation dates:

- Date of PD as indicated by target lesions: If PD is triggered by a change in sum of diameters of target lesions, and the dates of evaluation of the target lesions vary for the same assessment, assign the first evaluation date among target lesions.
- Date of PD as indicated by non-target lesions: If the dates of evaluation of the non-target lesions vary for the same assessment, assign the first evaluation date for which any non-target lesion exhibits a status of Unequivocal Progression.
- Date of PD as indicated by new lesions: If multiple new lesions are identified and the dates of evaluation for the new lesions vary for the same assessment, assign the first evaluation date for which any new lesion is detected.

In scenarios where the Investigator disease response is either a response or PD and differs from that of the application of RECIST v1.1 to investigator assessed tumor measurements separate response and/or progression dates will be required. Determination of the start date of a subsequently confirmed response in which the disease assessment spans multiple days remains the same as described previously. Specifically, the date of response assigned will be the latest date of evaluations corresponding to the disease assessment. The date of PD will be the earliest date of evaluations corresponding to the disease assessment.

### 7.2 Efficacy Criteria of Making an Internal Go Decision at an Interim Analysis

At an interim analysis, an internal Go decision may be made based on the delta ( $\Delta$ ), or difference, of the ORRs between durvalumab/novel agent combinations and durvalumab

alone. The internal Go decision may initiate further development of the combinations. The Go decision will not only be based on meeting the pre-specified efficacy criteria but also the totality of data including safety profiles, data from other studies, and internal portfolio prioritization.

For interim analyses that will lead to an internal Go decision, a response is defined as a confirmed CR or PR as per RECIST v1.1. The Lower Reference Value (LRV) is set to an 8% increase in  $\Delta$ ORR to demonstrate clinically meaningful increase over durvalumab alone. At final analysis, Go criteria will be met if the probability that the true  $\Delta$ ORR exceeds the prespecified LRV of 8% is more than 80% (i.e., Go:  $P[\Delta\text{ORR} > \text{LRV}] > 80\%$ ).

Early Go criteria are met if it is predicted that there is a high probability of reaching a Go decision upon full randomization of 60 subjects given the existing observed data (i.e., predictive probability of a Go decision  $> 95\%$ ). If Go criteria are met, randomization may continue, and planning activities for further development of the durvalumab/novel agent combination may be triggered.

[Table 7.2-1](#) illustrates the sample algorithm to make an early Go decision based on ORR at an interim analysis when control arm and an experimental arm each have 30 subjects.

**Table 7.2-1 Criteria of Early Go Decisions Based on ORR**

Number of Subjects with OR in Control Arm	Number of Subjects with OR in Experimental Arm
3	$\geq 12$
4	$\geq 13$
5	$\geq 14$
6	$\geq 16$
7	$\geq 17$
8	$\geq 18$
9	$\geq 19$
10	$\geq 20$
11	$\geq 21$
12	$\geq 22$
13	$\geq 23$
14	$\geq 24$
15	$\geq 25$
16	$\geq 25$
17	$\geq 26$
18	$\geq 27$
19	$\geq 28$
20	$\geq 28$
21	$\geq 29$

**Table 7.2-1 Criteria of Early Go Decisions Based on ORR**

Number of Subjects with OR in Control Arm	Number of Subjects with OR in Experimental Arm
22	30

ORR = objective response rate.

Operating characteristics of this continuous monitoring method are presented in [Table 7.2-2](#) based on 10000 simulations using the prespecified LRV.

**Table 7.2-2 Operating Characteristics of Continuous Monitoring for Go**

True $\delta$ (BM ORR = 30%)	All Go (Interim & final)	Early Go (Confirmed at final)
0%	3%	1% (0)
8%	19%	3% (3%)
15%	47%	10% (10%)
20%	69%	18% (17%)
25%	85%	31% (30%)

Criteria: Lower Reference Value (LRV)  $\delta = 8\%$ ; Go:  $\Pr(\delta > \text{LRV}) > 80\%$ ; Early Go:  $\text{PP}(Go) > 95\%$ ;  
BM ORR: Benchmark Objective Response Rate.

